4.4.6 STUDY EXIT

The study exit form will be completed when a participant exits the study. This form will be completed either at study completion, or if the participant is discontinued from the study at another time. A study exit form must be completed for all participants who have taken a study ID number. If, in the opinion of the investigator, post-study follow-up visits are required, the exit form will be completed after the last follow-up visit.

Exit monocular and binocular distance (HIHC VA logMAR) will be recorded with either the participant's spectacles, refraction or habitual contact lenses. An exit biomicroscopy assessment will be conducted if biomicroscopy has not already completed on the same day for a concurrent study visit.

After the exit assessments have been completed, the participant and investigator will complete the study completion and remuneration forms. At this time the participant will be considered as having exited the study.

4.4.7 UNSCHEDULED VISITS

An unscheduled visit is defined as an interim visit requested by the participant or investigator due to an unanticipated problem. Data recorded at these visits will be entered into the database. Only relevant and applicable unscheduled visit information will be included in the final report as deemed necessary by the lead investigator.

4.5 STUDY PROCEDURES

A summary of the study procedures to be conducted at the different scheduled visits is listed in Table 3. Most procedures are described in more detail in the following sub-sections.

Table 3: Summary of procedures to be conducted at scheduled visits

Procedure	Visit 1	Visit 2	Visit 3
	Screening	Baseline & Dispense	Day 14 Follow-up
Informed consent	X		

Participant demographics (age, sex)	X		
Medical history and medications	X		
Changes in medical history/medications			X
Contact lens history	X		
Digital device use history	X		
CLDEQ-8 questionnaire	X		
HIHC VA (logMAR) (habitual spectacles)	X		
Auto-refraction/auto-keratometry: horizontal and vertical K readings	X		
Non-invasive tear film break-up time	X		
Biomicroscopy	X		
Biomicroscopy (without lid margin staining)			X
Subjective refraction	X		
HIHC VA (logMAR) (study CL)	X	X	X
Study lens fitting	X		
Eligibility	X		
Subjective ratings (post-insertion comfort & vision)		X	
Subjective ratings (comfort, dryness, & vision)			X
Satisfaction ratings (Likert scale)			X
Lens assessment (fit, wettability, deposits)		X	X

Provide at-home ratings (comfort, dryness, & vision)		X	
Collect unused study lenses			X
Review of compliance (CL wear, digital device use, completion of at-home ratings)			X
HIHC VA (logMAR) (habitual spectacles or contact lenses)			X

4.5.1 CASE HISTORY

Demographics:

Demographic information from the participant will be obtained, including age and sex.

Medical History:

At screening, information will be obtained from the participant about the current medication, allergies, and any medical conditions. At the beginning of the Follow-up visits and end of study visits, the participant will be asked about changes in their medication or health.

Contact Lens History:

- Information will be obtained from the participant about the current contact lens type (lens brand name, lens power), replacement frequency, contact lens care solution (if applicable), typical number of lens wear days per week, typical lens wear time per day (total and comfortable), years of lens wear and use of artificial tears, plus confirmation that the subject uses contact lenses ≥ 13 hours per day;

Digital device use:

Participants will be asked about their typical use of digital devices (total hours/day of all devices combined) and to identify the type of devices (e.g. smartphone, computer, laptop, tablet) they use, with confirmation that the subject uses digital devices ≥ 8 hours per day.

4.5.2 CLDEQ-8 QUESTIONNAIRE

The Contact Lens Dry Eye Questionnaire (CLDEQ-8) is a validated questionnaire recommended by the 2013 TFOS Workshop on Contact Lens Discomfort¹² as the best approach for detecting

contact lens discomfort (CLD). Instructions for completion are present on the source documents and will be reviewed with the participant prior to completion. The CLDEQ-8 score ranges from 0 to 37, with higher scores indicating increased symptoms.

4.5.3 VISUAL ACUITY

Visual acuity for distance will be measured using high contrast computer-generated acuity charts in high illumination. Participants will be asked to read letters that progressively decrease in size on a computer screen located at a distance of 6 meters.

4.5.4 NON-INVASIVE TEAR FILM BREAK-UP TIME (NITBUT)

The participant will be seated in front of a device that will project rings of light (Placido discs) onto the tear film. The participant will be asked to keep their eyes open for as long as they can and the time until the rings first begin to distort, or break will be recorded. Three measurements will be taken to obtain an average value. The assessment will be carried out without study contact lenses.

4.5.5 AUTO-REFRACTION AND AUTO-KERATOMETRY

The participant will be asked to focus on a target while seated at an instrument that measures their approximate spectacle prescription and corneal shape.

4.5.6 SUBJECTIVE REFRACTION

The participant will be asked to read a letter chart from a distance through lenses placed in front of their eyes. They will also be asked to compare the clarity of their vision between different lenses placed in front of their eyes. This procedure aids in determining their spectacle and/or contact lens prescription.

4.5.7 SLIT LAMP BIOMICROSCOPY

A slit lamp biomicroscopy examination will be conducted to assess anterior segment ocular health. The participant will be seated behind a slit lamp and the ocular findings will be graded using Efron grading scale (0-4, 0.1 steps – unless otherwise stated).

External adnexa anomalies

The presence or absence of external adnexa anomalies will be recorded.

Bulbar and limbal hyperemia

The redness of each quadrant of the bulbar and limbal conjunctiva of both eyes will be assessed (Efron 0-4 scale; 0.1 increments).

Assessment of cornea and anterior eye for scars, infiltrates and any other abnormalities

The presence or absence of scars, infiltrates, or other abnormalities will be recorded. The size (diameter) of the largest infiltrate (0-4 where 0 = none, 1 = < 0.5mm, 2 = 0.5 – 1mm, 3 = 1 – 1.5 mm, 4 = >1.5 mm) and the depth of the largest infiltrate will be graded (0-4, 0 = none, 1 = epithelial, 2 = sub-epithelial, 3 = mid-stromal, 4 = deep stromal).

Corneal, conjunctival and lid margin staining

A sodium fluorescein strip, wetted with a few drops of saline, will be applied to the superior bulbar conjunctiva of both eyes. Staining of all five zones of the cornea and four zones of the conjunctiva will be graded while viewing with cobalt blue light through a Wratten no. 12 barrier filter (Efron 0-4 scale; 0.25 increments). The horizontal length (0-3 where 0 = <2mm, 1 = 2-4mm, 2 = 5-9mm, 3 = ≥10mm) and sagittal width (0-3 where 0 = <25%, 1 = 25-49%, 2 = 50-74%, 3 = ≥75%; 1 increment) of the staining of the upper and lower lid margins will be assessed.

Palpebral conjunctival hyperemia and roughness

The redness and roughness of the upper and lower eyelids (tarsal plate zone 2) will be assessed (Efron 0-4 scale; 0.25 increments).

4.5.8 LENS FIT & SURFACE ASSESSMENT

CL fit:

Lens fit will be assessed to ensure acceptable lens fit (centration and movement) with study lenses at the screening visit (V1).

At V2 and V3, lens centration and movement will be assessed as follows:

- *Lens centration (0-3 scale; 0 = optimal, 1 = slight decentration, 2 = moderate decentration but not encroaching limbus; 3 = excessive & occasionally encroaching limbus);*
- *Lens movement for primary gaze (+2 to -2 scale; -2 = unacceptably tight, -1 = slightly tight but acceptable, 0 = optimal, +1 = slightly loose but acceptable, +2 = unacceptably loose);*
- *Lens tightness on push-up test (0-100 scale; 0 = falls from cornea without lid support; 50 = optimal, 100 = no movement).*

CL surface wettability and deposits:

Contact lens wettability and deposits will be graded with study lenses at V2 and V3:

- *Surface wettability (0-4 scale in 0.25 steps; 0 = excellent); very low illumination, external diffuser in place, x32 magnification, viewing the quality of the Purkinje image;*
- *Surface deposits (0-4 scale in 0.25 steps; 0 = excellent); using low illumination and a moderate beam with direct illumination to scan the contact lens for deposits, x32.*

4.5.9 SUBJECTIVE RATINGS

Subjective ratings:

At visit 2, participants will be provided with subjective rating questionnaires using a 0-100 scale (where 100 = best performance; integer steps, both eyes rated together) to assess their first impression with the study CLs post-insertion regarding comfort and clarity of vision.

At the end of Visit 2, participants will be provided with at-home questionnaires to subjectively rate the experience with study lenses regarding comfort, dryness, and clarity of vision using a 0-100 scale (integer steps; both eyes together), where 100 means better performance. This questionnaire will be completed on Days 1, 7, and 14 ± 1 after Visit 2 (i.e. Day 0), at three different time-points on each of these days: after insertion, after 8 hours of digital device use, and at the end of the day just before lens removal. The final at-home questionnaire will be the evening before their scheduled Visit 3. In addition, times of lens insertion, first notice of discomfort, and lens removal will be collected. There will also be a diary entry for the number of hours of cumulative digital device use that day.

At Visit 3, participants will be provided with subjective rating questionnaires to assess a typical day over the past 2 weeks, to report their experiences i) 5 minutes after insertion, ii) after 8 hours of digital device use, iii) at the end of the day just prior to lens removal, and iv) overall. For each typical timepoint, comfort, dryness, and clarity of vision will be assessed using a 0-100 scale (integer steps; both eyes together), where 100 means best performance.

Satisfaction with study CL:

Satisfaction (5-point Likert scale: strongly disagree, slightly disagree, neither disagree or agree, slightly agree, strongly agree) with DAILIES TOTAL1® CLs overall and while using digital devices on a typical day in the past 2 weeks will be assessed for the following questions:

- *The study lenses provide good vision all day long.*
- *The study lenses provide good comfort all day long.*

- *I am satisfied with the comfort the study lenses provide when I use digital devices for ≥ 8 hours.*
- *I am satisfied with the vision the study lenses provide when I use digital devices for ≥ 8 hours.*
- *I don't experience eye strain when I wear the study lenses and use digital devices for ≥ 8 hours.*
- *I don't experience eye fatigue (tired eyes) when I wear the study lenses and use digital devices for ≥ 8 hours.*
- *I don't experience episodes of blurred vision when I wear the study lenses and use digital devices for ≥ 8 hours.*
- *I don't experience dryness with digital device use.*
- *Overall, these lenses provide good performance when using digital devices for ≥ 8 hours.*

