4.2.3 INCLUSION AND EXCLUSION CRITERIA

A person is eligible for inclusion in the study if they:

1. Are between 18 and 40 years of age (inclusive) and has full legal capacity to volunteer;
2. Have read and signed an information consent letter;
3. Are willing and able to follow instructions and maintain the appointment schedule;
4. Are a digital device user (at least 8 hours on a typical day using any combination of digital devices such as PC, laptop, smartphone or tablet);
5. Are a habitual wearer of daily wear, spherical, soft contact lenses (no bifocal or multifocal contact lenses, no extended wear or monovision) for at least 5 days/week and at least 13+ hours/day on a typical day during the month prior to enrolment;
6. The habitual lens type brand will be restricted such that a maximum of 7 participants will be included in the study for each lens brand/material;
7. Have a vertex corrected spherical equivalent distance refraction within -0.50D to -9.00D in each eye;
8. Have a vertex corrected refractive cylinder ≤ -0.75 cylindrical correction in each eye after vertexing to the corneal plane;
9. Demonstrate an acceptable fit and achieves best corrected visual acuity of at least 0.10 logMAR in each eye with DAILIES TOTAL1® contact lenses;

10. Are willing to wear DAILIES TOTAL1® contact lenses at least 5 days per week and 13+ hours per day throughout the study.

A person will be excluded from the study if they:

1. Are participating in any concurrent clinical or research study involving intervention or invasive ocular tests;
2. Are presbyopic or habitually use a reading addition for close work;
3. Have any known active* ocular disease and/or infection;
4. Meet the diagnosis of dry eye disease as per the following combination:
 - Meets the symptom criteria of CLDEQ-8 score ≥ 12
 - And they show 1 of the following 2 signs:
 - Either NaFl staining (either [cornea >5 dots] or [conjunctiva >9 dots] or [lid margin >2 mm length AND $\geq 25\%$ width]);
 - Or NITBUT (no contact lens) <10 seconds.
5. Have a systemic condition that in the opinion of the investigator may affect a study outcome variable;+
6. Are using any systemic or topical medications that in the opinion of the investigator may affect a study outcome variable;
7. Are a current wearer of DAILIES TOTAL1® daily disposable contact lenses;
8. Have known sensitivity to the diagnostic pharmaceutical sodium fluorescein to be used in the study;
9. Have undergone refractive error surgery;

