10 STATISTICAL ANALYSIS AND DATA MANAGEMENT

10.1 STATISTICAL ANALYSIS

All data will be analyzed by CORE at the University of Waterloo. Unmasked data analysis will be conducted using Statistica, SPSS, or other appropriate software. Descriptive statistics will be provided on information regarding baseline variables (age, sex, refractive error distribution, etc.).

Descriptive statistics will be provided for all primary and exploratory outcomes as well as information regarding baseline variables (e.g. age, sex).

Subjective ratings and lens fit assessments will be compared between Visit 2 (Dispense) and Visit 3 (2-week follow-up) using either paired t-tests or Wilcoxon matched pairs, or using ANOVA, as applicable; statistical significance will be set at 5%. The appropriate tests will be

selected based on tests of normality – non-parametric tests will be used for data not showing a normal distribution. For assessments conducted for each eye separately, the right eye will be used for analysis if there is no difference between the eyes.

Binomial testing will be conducted to analyze Likert questionnaires. For example, agreement questionnaires (strongly disagree, slightly disagree, neither disagree nor agree, slightly agree, strongly agree) to determine whether participants had a positive or negative experience with the test lens.

Additional analysis may be conducted.

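### The Likert dryness item omits the 8-hour condition its sister items carry, so it is not strictly comparable with them

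*Combined protocol and SAP*

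**What the plan says.** Section 4.5.9, under the label "Satisfaction with study CL", lists nine statements answered on a five-point agreement scale at Visit 3. The stem names the study lens and sets the scope as follows: "CLs overall and while using digital devices on a typical day in the past 2 weeks will be assessed for the following questions".

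In the dryness statement, the participant does not "experience dryness with digital device use". The neighbouring symptom statements are more specific. The eye strain item is that the participant does not "experience eye strain when I wear the study lenses and use digital devices for ≥ 8 hours", and the blur item that they do not "experience episodes of blurred vision when I wear the study lenses and use digital devices for ≥ 8 hours". The eye fatigue item has the same ending.

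Section 10.1 states: "Binomial testing will be conducted to analyze Likert questionnaires". It gives the purpose as deciding whether participants' experience with the test lens was positive or negative. Section 2 places the Likert items among the other outcomes of interest, not the primary ones.

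**The concern.** The study question is about lens performance on days with at least 8 hours of device use. That condition appears in the objective and primary outcomes (Section 2) and in the hypothesis (Section 3). The authors repeated it in every other device-use Likert item, and nothing in the protocol explains why the dryness item lacks it. It looks like a drafting slip.

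Taken as written, the item asks about dryness during device use of any length. A participant who has no dryness in a short session but does have it late in a long day could reasonably agree. The strain, fatigue and blur items do not leave that room. If the four symptom items are tested and reported side by side, a reader will assume that they share a condition, and one of them does not. Dryness is one of the three primary domains, and this is the only Likert item on it, so the result is likely to be read with some interest.

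**Working it through.** No figure in the plan depends on this item, so the check compares texts.

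**Step 1. Classify the nine items in Section 4.5.9.**

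| Item | Subject | Names the lenses | States 8 hours or more |
|---|---|---|---|
| 1 | Vision through the day | Yes | No (general item) |
| 2 | Comfort through the day | Yes | No (general item) |
| 3 | Comfort with devices | Yes | Yes |
| 4 | Vision with devices | Yes | Yes |
| 5 | Eye strain | Yes | Yes |
| 6 | Eye fatigue | Yes | Yes |
| 7 | Blurred vision | Yes | Yes |
| 8 | Dryness | No | No |
| 9 | Overall performance with devices | Yes | Yes |

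Eight of nine items name the lenses. Of the seven device-use items (3 to 9), six state the hours. The dryness item is the exception on both counts.

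**Step 2. See what the surrounding text supplies.** The label and stem give the study lens, device use, a typical day and the two-week recall period. They give no number of hours.

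**Step 3. See whether the entry criterion fills the gap.** Section 4.2.3 requires "at least 8 hours on a typical day using any combination of digital devices". That describes total use over a day and decides who is enrolled. It does not tell a participant which part of the day, or how long a period of use, to have in mind when answering item 8. On a day that reaches 8 hours, the item can still be answered about the first hour or two.

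**Step 4. Ask what else measures dryness under the intended condition.**
- Section 2: overall dryness on a typical day with 8 or more hours of device use is a primary 0-100 rating.
- Sections 4.4.5 and 4.5.9: at Visit 3, dryness is also rated for a typical day after 8 hours of device use.
- Sections 4.4.4 and 4.5.9: at home, dryness is rated after 8 hours of device use on Days 1, 7 and 14±1.

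**Step 5. Consider direction.** If dryness builds up with hours of use, which is an assumption, answers about shorter sessions would make agreement easier and the item would flatter the lens relative to items 5 to 7. The documents give no data from which to size this.

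**The case against.** The strongest reply is that the stem governs every item below it. It names the lens and refers to a typical day, and people are enrolled because their typical day contains at least 8 hours of device use. Typical device hours are also reviewed at Visit 3 (Section 4.4.5). On that reading item 8 already means what its neighbours say.

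For the lens, most of this stands. A reader might infer from the bare wording that the test does not measure dryness with DAILIES TOTAL1, or that the result cannot be attributed to the lens. The documents do not support that, because the label and stem both name the study lens. The participant-facing form is not in the documents, so it cannot be seen whether the stem is printed above the items. That leaves some uncertainty but is not evidence of a fault.

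For the hours, the reply is weaker. The condition is at best implied, and the authors did not rely on implication in the other six device-use items.

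Two numerical arguments might also tempt a reader, and neither measures the size of this problem:
- Wear is required on at least 5 days a week, so 14 − 10 = 4 days could pass without study lenses. That is a permitted maximum, and the stem directs the answer to the study lens.
- With 32 completers, an assumed null proportion of 0.5 and a two-sided test, 22 positive answers give p = 0.0501 and 23 give p = 0.020, so one answer can cross the 5% line. Section 10.1 states neither the null nor the sidedness for these tests. The boundary is the same for all nine items and would not move if item 8 were reworded.

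**Conclusion.** The point holds in a limited form. The dryness item is less specific than the other device-use items. The missing lens reference is largely repaired by the stem, while the missing 8-hour condition is not. The item's binomial result is therefore not strictly comparable with the results for strain, fatigue and blur, and should not be described as dryness under 8 or more hours of use.

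The consequence is small: one of nine items in a non-primary outcome. No primary outcome, hypothesis or sample size depends on it, and the dryness ratings on the 0-100 scale cover the intended condition directly. Those ratings do not repair the Likert result, which will be tested in its own right. The conclusion assumes that the form uses the wording in Section 4.5.9. If the form already states the hours, only the protocol text needs correcting.

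**What to change.** Before first use, give item 8 the wording of the eye strain item, with dryness in place of eye strain, so that it names the study lenses and the 8-hour condition. Make the same change in Section 4.5.9 and on the questionnaire. Confirming that the stem is printed on the form is worthwhile, but it would settle only the lens reference and not the hours.

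The cost is one line in each place. Sample size, visits and tests do not change. If the earlier lens study used the present wording, word-for-word comparability of this one item would be lost. The documents do not say whether it did, and no such comparison is planned.

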5 MONITORING PROTOCOL ADHERENCE

All personnel involved in this study will be listed on a delegation log and their training will be documented. Consent documentation will be reviewed by personnel not involved in the consent process. Visit windows will be reviewed when determining the analysis cohort. All adverse events and protocol deviations will be reviewed by the Lead Investigator. Serious and significant adverse events and major protocol deviations will be reviewed by the Principal Investigator and Head of Clinical Research.

6 POTENTIAL RISKS AND BENEFITS TO HUMAN PARTICIPANTS

This is a minimal risk study because of the use of marketed products and standard optometric assessments.

Contact lenses in this study will be worn on a daily wear and daily disposable basis. Adverse events and/ or complications in daily wear of soft contact lenses can occur (e.g.: inflammation and infection). Complications that may occur during the wearing of contact lenses include discomfort, dryness, aching or itching eyes, excessive tearing, discharge, hyperemia and variable or blurred vision. More serious risks may include photophobia, iritis, corneal edema or eye infection. Although contact lens-related infections are very infrequent, the possibility does exist. The incidence of infection due to daily-wear soft lenses is 0.035%. Almost always an infection will occur only in one eye. Thirty five million Americans who currently wear contact lenses assume this risk.

When contact lenses are worn on a daily wear basis there is a small risk of an adverse event compared to not wearing contact lenses.

A dye (fluorescein) normally used for eye exams is being used in this study. Although rare, it is possible that participants may have an allergic reaction to the dye. This could cause discomfort to their eye.

Additionally, it is possible that participants may experience temporary discomfort associated with the study procedures/ products including: burning and stinging, blurred vision, sandiness or grittiness, light sensitivity, dryness, itching, crusty eyes and foreign body sensation.

This study will be conducted during the ongoing COVID-19 pandemic. Therefore, risks of infection with COVID-19 exist through participation. These risks arise due to possible exposure during commute to and from the study visit as well as during the study visit, particularly due to the closeness of the investigator and participant (within 2m for some assessments). The potential effects of COVID-19 are not yet fully known and may include long-term health consequences. In a small percentage, infection with COVID-19 can lead to serious illness, hospitalization, and in rare cases to complications leading to death. Individuals aged 60 and above and those with underlying medical conditions are considered at a greater risk for severe illness from the COVID-19 virus however they are excluded from this study for different reasons.

In consideration of risks associated with COVID-19, CORE has implemented a series of on-site safety procedures which have been reviewed and approved by the University of Waterloo. These include, but are not limited to, self-screening of investigators, maintaining physical distancing as much as possible, frequent handwashing, wearing of face masks by the investigator and participant as per University guidelines, and frequent room and equipment hygiene. In addition, members of CORE and participants will follow any University policies regarding Covid-19 vaccination.

Participants may not benefit directly from taking part in this study. Information from this study may help researchers come up with new soft contact lens designs to help others in the future. This study may help the research team to better understand the performance of the product being used in this study, particularly during digital device use.

